### 5.2.3 Incidence of AKI

The incidence of AKI post-cardiac surgery through Day 5 will be defined as:

- An absolute increase from baseline to  $\geq 1.5 \times$  Baseline at any time; or
- A documented AE of sustained reduction in urine output, oliguria, or anuria; or
- Initiation of dialysis

## 5.3 Exploratory Efficacy Endpoints

### 5.3.1 Severity of AKI

Maximum severity of AKI post-cardiac surgery through Day 7 will be a categorical variable. It is defined as the maximum severity over Days 2 through 7 for subject with AKI incidence PostOp through Day 7 (replacing Day 5 with Day 7 in Section 5.2.3) as follows:

Stage 1      if  $\text{Creat}_{\text{Di}} - \text{Creat}_{\text{BL}} \geq 0.3 \text{ mg/dL}$ , or

	$1.5 * \text{Creat}_{\text{BL}} \leq \text{Creat}_{\text{Di}} < 2 * \text{Creat}_{\text{BL}}$ (i=2 to 7)
Stage 2	if $2 * \text{Creat}_{\text{BL}} \leq \text{Creat}_{\text{Di}} < 3 * \text{Creat}_{\text{BL}}$ (i=2 to 7)
Stage 3	if $\text{Creat}_{\text{Di}} - \text{Creat}_{\text{BL}} \geq 4$ mg/dL, or $3 * \text{Creat}_{\text{BL}} \leq \text{Creat}_{\text{Di}}$ (i=2 to 7), or need for dialysis and date of dialysis < date of surgery +6

where  $\text{Creat}_{\text{BL}}$  is creatinine at baseline (Day 1 PreOp),  $\text{Creat}_{\text{Di}}$  is creatinine on Day  $D_i$  (i.e., Days 2, ..., 7).

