## 7.5.3 Exploratory Analysis

### 7.5.3.1 Severity of AKI

Maximum severity of AKI through Day 7 will be summarized by presenting the proportion of subjects in each severity stage in each treatment group. CMH test for the row mean score difference will be used for the between active treatment and placebo difference stratified by the surgery type and time on pump. A modified ridit score will be used in the CMH test.

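### AKI severity is scored only for subjects who have AKI, so the exploratory between-arm test, read literally, compares a post-randomisation subset, and some AKI subjects get no stage

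*SAP*

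**What the plan says.** SAP 5.3.1 defines the endpoint: "It is defined as the maximum severity over Days 2 through 7 for subject with AKI incidence PostOp through Day 7". Three stages follow. Each rests on serum creatinine, apart from one further route into Stage 3: "need for dialysis and date of dialysis < date of surgery +6". There is no category for absence of AKI. The creatinine baseline in this section is Day 1 PreOp.

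Entry to the scale is through SAP 5.2.3, with the window extended from Day 5 to Day 7. AKI is a creatinine value of at least 1.5 times baseline, or dialysis, or "A documented AE of sustained reduction in urine output, oliguria, or anuria". Section 5.2.3 names no special baseline, so the general definition in SAP 4.1 (last value before dosing, usually Visit 1a) applies.

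SAP 7.5.3.1 plans a summary by "presenting the proportion of subjects in each severity stage in each treatment group", with no denominator stated. On testing it says: "CMH test for the row mean score difference will be used for the between active treatment and placebo difference". The test is stratified by surgery type and pump time, and "A modified ridit score will be used in the CMH test". SAP 7.5 assigns all efficacy endpoints other than the primary to the MITT population.

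**The concern.** A subject with no value on the scale cannot contribute to a row mean score test. On the literal text, the arms are therefore compared among AKI cases only. Protocol 6.4 hypothesises that RBT-1 lowers AKI incidence, so membership of the compared set is itself an expected effect of treatment, and the protection of randomisation is lost. Two consequences follow. A drug that prevents AKI equally at every stage leaves the distribution among cases unchanged, so the test cannot see the benefit. A drug that prevents mainly mild AKI leaves a smaller and, on average, more severe group of cases, so the test can lean against it.

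Separately, the stages do not cover every route into AKI. Some subjects who count as AKI cases cannot be placed on the severity scale at all.

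**Working it through.** The documents give no power, effect or sample-size figure for AKI severity, so there is no stated figure to reproduce.

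**Inputs from the documents.** 42 subjects per arm (Protocol synopsis). Background AKI incidence of about 30% (Protocol 6.1), used here as the placebo rate, although it is quoted beside KDIGO criteria and not the SAP 5.2.3 definition. Three pump-time categories (SAP 7.5). Three surgery types, taken from the subgroup list in SAP 7.5.3.5 because 7.5.3.1 does not define the levels.

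**Assumed inputs.** The split of placebo AKI over Stages 1 to 3, and the pattern of drug effect. The documents give neither.

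**Mean stage.** Let p1, p2, p3 be the percentages of an arm in Stages 1, 2 and 3. Among cases, mean stage = (p1 + 2·p2 + 3·p3)/(p1 + p2 + p3). Over all subjects, with no AKI = 0, mean stage = (p1 + 2·p2 + 3·p3)/100. With a placebo split of 20/6/4%:

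| Arm and pattern | Stage 1/2/3, % of arm | Mean among cases | Mean over all subjects |
|---|---|---|---|
| Placebo | 20/6/4 | 44/30 = 1.467 | 0.44 |
| RBT-1, Stage 1 halved | 10/6/4 | 34/20 = 1.70 | 0.34 |
| RBT-1, every stage halved | 10/3/2 | 22/15 = 1.467 | 0.22 |
| RBT-1, half of each stage moved down one step | 13/5/2 | 29/20 = 1.45 | 0.29 |

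Over all subjects RBT-1 is better in every row. Among cases it looks worse in the first pattern, identical in the second and almost identical in the third.

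**Subjects used.** In the first pattern the expected number of cases is 42 × 0.30 + 42 × 0.20 = 12.6 + 8.4 = 21 of the 84 subjects in a two-arm comparison, or 25%. With nine equal strata, about 14 of the 21 fall in strata that contain cases from both arms.

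**Simulation of the CMH row mean score test with modified ridit scores.** All runs have 42 per arm and prevention confined to Stage 1.

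- Split 20/6/4%, nine strata, half of Stage 1 prevented: the cases-only statistic points against RBT-1 in about 70% of trials; the all-subject statistic points in favour in 82%.
- Placebo AKI 30%, splits among cases of 60/25/15, 70/20/10 and 80/15/5, unstratified, half of Stage 1 prevented: cases-only points against RBT-1 in 77%, 75% and 72%. It is significantly against in 10 to 12%, where 2.5% is nominal. The all-subject version points in favour in 79 to 88%.
- Split 70/20/10, nine strata: against RBT-1 in 71%, significantly so in about 7%.
- Split 70/20/10, placebo AKI varied from 15% to 40%, unstratified: against RBT-1 in 67% to 79%.

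**Who gets no stage.**

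- *Urine output alone.* A subject with a qualifying adverse event, a creatinine rise below 0.3 mg/dL, a ratio below 1.5 and no dialysis has AKI under 5.2.3 but meets no stage in 5.3.1.
- *Different baselines.* Let B be the Visit 1a creatinine and r·B the Day 1 PreOp value, with r between 1 and 1.5. A postoperative value of 1.5·B qualifies as AKI. Against the staging baseline the ratio is 1.5/r, which is below 1.5, and the rise is (1.5 − r)·B. If that rise is below 0.3 mg/dL, no stage applies.
- *Dialysis window.* SAP 4.2 makes the day of surgery Day 1, so Day 7 is the surgery date + 6. A strict inequality at + 6 ends at Day 6, while the endpoint runs through Day 7. Dialysis first given on Day 7 meets the entry criterion but not the dialysis route to Stage 3.

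**The case against.** The SAP nowhere says that subjects without AKI are dropped. Section 7.5 points to MITT, and 7.5.3.1 states no case-only denominator, so a programmer could reasonably add a zero category. This stands in part: exclusion is the literal consequence of 5.3.1, not an explicit instruction. But the MITT assignment gives these subjects no severity value, and the two readings can differ in sign, so the choice should not be left to programming.

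A reader might infer that the endpoint generally points the wrong way. The documents do not support that. The reversal needs prevention concentrated in Stage 1; the other two patterns in the table show insensitivity, not reversal. A reader might also take 70% as the chance of a misleading finding. It is only the sign of the statistic, under assumed inputs; the significantly adverse rate with half of Stage 1 prevented is about 7 to 12%. Nor can the loss of about three quarters of subjects be stated as fact, since it depends on the borrowed 30% rate and the assumed effect.

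The practical stakes are limited. The endpoint is exploratory. The table list in SAP Section 8 has no severity table, and only Listing 16.2-2.5.2 carries severity. AKI incidence is tested separately in MITT as a secondary endpoint, so a reader would see any fall in incidence alongside. The urine-only gap is narrow, and its frequency cannot be estimated from the documents. All of this stands and limits the weight of the point. It does not remove the defect, because 7.5.3.1 still prescribes a formal between-arm test.

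**Conclusion.** The point holds as a defect of definition with modest impact. Read literally, SAP 5.3.1 and 7.5.3.1 confine the severity comparison to a subset selected after randomisation on the outcome the drug is expected to change. The comparison is blind to a uniform reduction in AKI and can lean against RBT-1 if mild AKI is what is prevented. The size of the reversal rests on an assumed stage split, a placebo rate borrowed from the protocol background, and an effect confined to Stage 1.

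The gap for AKI by urine output alone follows from the text without any assumption. The baseline and dialysis-window mismatches can leave further AKI subjects unstaged; how many cannot be judged from the documents. It might be inferred that urine-only cases simply belong in Stage 1, but nothing in the documents settles their class, so it has to be an explicit choice.

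**What to change.** In SAP 5.3.1, define an ordinal score from 0 to 3 for every MITT subject, with 0 meaning no AKI under 5.2.3 through Day 7. In 7.5.3.1, run the CMH row mean score test on that score, state the denominator for the stage proportions, and keep the distribution among AKI cases as descriptive only.

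Before unblinding, also:

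- Pre-specify one category for AKI by urine output alone, for example the lowest AKI category, with a sensitivity analysis that places it differently.
- State how a death without AKI is scored; otherwise it would fall in the best category.
- Reconcile the creatinine baseline and the dialysis window between 5.2.3 and 5.3.1, so that every subject counted as AKI through Day 7 receives a stage.

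The cost is a few sentences in 5.3.1 and 7.5.3.1, plus one table in Section 8 if the test is to be reported. No new data are needed.

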## **4 DEFINITIONS**

### **4.1 Baseline**

Baseline is defined as the last value collected prior to the start of the study drug administration, unless specified otherwise. This usually is the value collected at Visit 1a Predose for vital signs, serum chemistry, hematology, and blood and urine biomarkers. If missing, then the value collected at unscheduled visit or Visit 0, whichever is available and more recent to study drug administration, will be used.

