### 5.3.3 Occurrence of MAKE

Endpoints related to MAKE are as follows:

- Proportion of subjects experiencing either MAKE30, MAKE60, or MAKE90
- Proportion of subjects experiencing MAKE30
- Proportion of subjects experiencing MAKE60
- Proportion of subjects experiencing MAKE90

MAKE30 is defined for subjects with AKI incidence PostOp through Day 5 as follows

- Death (of all cause) and date of death < date of surgery + 30, or
- Need for dialysis and date of dialysis < date of surgery + 30, or
- $(\text{eGFRD}_{30} - \text{eGFR}_{\text{BL}}) / \text{eGFR}_{\text{BL}} \leq -0.25$  PostOp through Day 30

MAKE60 is defined for subjects with AKI incidence PostOp through Day 5 as follows

- Death (of all cause) and date of death < date of surgery + 60, or
- Need for dialysis and date of dialysis < date of surgery + 60, or
- $(\text{eGFRD}_{60} - \text{eGFR}_{\text{BL}}) / \text{eGFR}_{\text{BL}} \leq -0.25$  PostOp through Day 60

MAKE90 is defined for subjects with AKI incidence PostOp through Day 5 as follows

- Death (of all cause) and date of death < date of surgery + 90, or
- Need for dialysis and date of dialysis < date of surgery + 90, or
- $\text{eGFRD}_{90} - \text{eGFR}_{\text{BL}} / \text{eGFR}_{\text{BL}} \leq -0.25$  PostOp through Day 90

where  $\text{eGFR}_{\text{BL}}$  is eGFR at baseline (Day 1 PreOp),  $\text{eGFR}_{30}$ ,  $\text{eGFR}_{60}$ , and  $\text{eGFR}_{90}$  are eGFR on Days 30, 60, and 90, respectively. Note, eGFR (mL/min/1.73m^2) is calculated using 2009 CKD-EPI equation:

$$141 \times \min(S_{\text{Cr}}/\kappa, 1)^{\alpha} \times \max(S_{\text{Cr}}/\kappa, 1)^{-1.209} \times 0.993^{\text{Age}} \times 1.018 \text{ [if female]} \times 1.159 \text{ [if African American]}.$$

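### AKI severity and the MAKE eGFR criterion admit subjects on a pre-dose baseline but judge them against post-dose Day 1 PreOp, and the Stage 3 dialysis window closes a day early

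*SAP*

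**What the plan says.** **Default baseline.** SAP 4.1: "Baseline is defined as the last value collected prior to the start of the study drug administration, unless specified otherwise". It adds that this is usually the Visit 1a value.

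**Entry.** The first AKI criterion in SAP 5.2.3 begins "An absolute increase from baseline to" and sets the bar at 1.5 times Baseline. It names no visit, so the 4.1 default applies. (SAP 2.2 makes clear that serum creatinine is meant.) Subjects can also enter through a urine-output adverse event or the start of dialysis.

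**Severity.** SAP 5.3.1 stages AKI "for subject with AKI incidence PostOp through Day 7 (replacing Day 5 with Day 7 in Section 5.2.3". Its reference, Creat_BL, "is creatinine at baseline (Day 1 PreOp". The Stage 3 dialysis limb reads "need for dialysis and date of dialysis < date of surgery +6".

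**MAKE.** SAP 5.3.3: "MAKE30 is defined for subjects with AKI incidence PostOp through Day 5 as follows", and the same for MAKE60 and MAKE90. The eGFR limb asks for a fall of at least 25% from eGFR_BL, which "is eGFR at baseline (Day 1 PreOp". The dialysis limb reads "Need for dialysis and date of dialysis < date of surgery + 30, or".

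**Elsewhere.** SAP 5.3.2, 7.5.3.2 and 7.5.3.3 use Visit 1a for change in creatinine and eGFR. SAP 7.5.3.2 counts Day 1 among the post-dose visits. Dosing is 24 to 48 hours before surgery (Protocol 9.5.4; SAP 2.1).

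**The concern.** Stage 1 starts at 1.5 times baseline, the same multiple as the creatinine entry criterion. With one baseline, every subject admitted on creatinine has at least Stage 1. With two, that no longer follows: a subject can count as AKI yet meet no stage, or land in a different stage, because creatinine moved between Visit 1a and PreOp. For MAKE, the same Day 30, 60 or 90 eGFR is summarised against Visit 1a in 7.5.3.3 and tested for a 25% loss against PreOp in 5.3.3.

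The dialysis limb raises a separate question of dates: whether it covers the whole period that the severity endpoint claims to cover.

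**Working it through.** **1. Dialysis window.** SAP 4.2 makes Day 1 the day of surgery, so Day k = surgery date + (k − 1). A rule of the form date < surgery + c has its last qualifying date at surgery + (c − 1), which is Day c.

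| Rule | Last day included | Endpoint runs through |
|---|---|---|
| Stage 3 dialysis, < surgery + 6 | Day 6 | Day 7 |
| MAKE30, < surgery + 30 | Day 30 | Day 30 |
| MAKE60, < surgery + 60 | Day 60 | Day 60 |
| MAKE90, < surgery + 90 | Day 90 | Day 90 |

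Only the Stage 3 rule falls short. A subject first dialysed on Day 7 who reaches neither 3 times baseline nor +4 mg/dL is admitted as AKI through Day 7 but does not meet Stage 3.

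**2. Staging.** The rule in 5.3.1 is applied to illustrative creatinine values in mg/dL. The documents do not say how far PreOp departs from Visit 1a.

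| Visit 1a / PreOp / peak | Against Visit 1a | Against PreOp |
|---|---|---|
| 0.9 / 1.08 / 1.35 | 1.50x: admitted, Stage 1 | 1.25x, +0.27: no stage |
| 1.0 / 1.1 / 2.1 | 2.10x: Stage 2 | 1.91x: Stage 1 |
| 1.0 / 0.9 / 1.9 | 1.90x: Stage 1 | 2.11x: Stage 2 |

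The no-stage case is narrow. It needs PreOp > max(peak − 0.3, peak/1.5). For a peak of exactly 1.5x:
- Visit 1a 0.7: peak 1.05, so PreOp above 0.75 (+7.1%).
- Visit 1a 0.9: peak 1.35, so PreOp above 1.05 (+16.7%).
- Visit 1a 1.0: peak 1.50, so PreOp above 1.20 (+20%).

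At Visit 1a 1.0 and a peak of 1.8, PreOp would have to exceed 1.50 (+50%).

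**3. MAKE eGFR limb.** The equation is the CKD-EPI 2009 form printed in 5.3.3. Kappa (0.7 women, 0.9 men) and alpha (−0.329 women, −0.411 men) are printed only in SAP Appendix B and are taken as intended. When both creatinine values are at or above kappa, age and sex cancel and the eGFR ratio is (creatinine ratio)^−1.209. A 25% loss then needs a creatinine ratio of at least 0.75^(−1/1.209) = 1.269.

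Two illustrations (Visit 1a / PreOp / Day 30), for men already admitted as AKI by Day 5:
- 1.0 / 1.1 / 1.3: 1.3^−1.209 − 1 = −27.2% against Visit 1a (met); (1.3/1.1)^−1.209 − 1 = −18.3% against PreOp (not met).
- 1.0 / 0.9 / 1.15: −15.5% against Visit 1a (not met); (1.15/0.9)^−1.209 − 1 = −25.6% against PreOp (met).

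The 1.269 multiple does not hold below kappa. For a man at 0.80, the kappa term is (0.80/0.9)^−0.411 = 1.050. The target is 0.75 × 1.050 = 0.787, so the later creatinine is 0.9 × 0.787^(−1/1.209) = 1.097, which is 1.37x baseline. Because 7.5.3.2 puts the lowest approximate tertile of baseline creatinine at 0.9 mg/dL or less, this applies to a real share of men.

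**The case against.** The strongest reply is that PreOp is a deliberate and legitimate choice. Section 4.1 allows exceptions, 5.3.1 and 5.3.3 name PreOp explicitly, both endpoints concern injury after surgery, and PreOp is the last scheduled creatinine before it. Visit 1a would bring in pre-operative drift. Much of this stands: naming PreOp is not an error. But it does not explain why entry and grading use different references, and a sentence of rationale would not restore a stage to every subject admitted on creatinine.

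It is also fair that 7.5.3.3 is a mean-change analysis with no 25% threshold, so it does not contradict a MAKE call; it only reports the same values on another reference. The mismatch touches only the creatinine entry route. The death and dialysis limbs of MAKE use no baseline. Section 8 lists a table for MAKE, while severity appears only in a listing, although 7.5.3.1 still plans a test.

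Three stronger readings are tempting:
- **That the PreOp reference biases the results or favours an arm.** PreOp can lie above or below Visit 1a, subjects move in both directions, and the documents give no drift by arm.
- **That the SAP breaches Protocol 11.3**, which sets a pre-dose baseline for all endpoints. SAP section 1 says that the SAP prevails where the two differ.
- **That post-surgical values generally enter the baseline through the interpolation rule in 7.2.** That rule first takes the local result and interpolates only if there is none. The documents do not suggest that this would be common.

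**Conclusion.** The mismatch and the date slip are both present in the current text and should be corrected. The mismatch can leave an admitted subject without a stage, shift a stage either way, or change whether the MAKE eGFR limb is met. The date slip affects only subjects first dialysed on Day 7 who do not reach Stage 3 on creatinine.

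The consequence is limited. Both endpoints are exploratory, no arm-specific bias is shown, and the primary and secondary tests do not use these definitions. The worked values are illustrations. They rest on assumed movement between Visit 1a and PreOp, so the number of subjects affected cannot be estimated from the documents. The reading of 5.2.3 rests on the 4.1 default, since 5.2.3 names no visit.

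**What to change.** - In SAP 5.3.1 and 5.3.3, define Creat_BL and eGFR_BL as the pre-dose baseline of 4.1 (Visit 1a), and name that baseline in 5.2.3.
- Keep Day 1 PreOp as a sensitivity analysis for both endpoints, using measured central or local values only and no interpolated ones. Report how many subjects have neither.
- Change the Stage 3 dialysis limb to a date before surgery date + 7, the convention by which the MAKE30 rule includes Day 30.

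The cost is SAP wording and derivation code; creatinine at both visits is already collected. The downside is that Visit 1a includes pre-operative drift unrelated to surgery, which the PreOp sensitivity analysis addresses. No change to 7.2 is needed for these endpoints: with Visit 1a as baseline and measured PreOp in the sensitivity analysis, an interpolated PreOp value cannot serve as the baseline in either. Barring interpolation there would also alter Day 1 handling in the repeated-measures models of 7.5.3.2 and 7.5.3.3.

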### 5.3.2 Mean increase from Baseline in Serum Creatinine

Mean increase in serum creatinine will be computed as the average of the post-baseline serum creatinine through Day 7 or Discharge, whichever is earlier, minus baseline serum creatinine. Baseline is defined as the serum creatinine collected at Visit 1a time point.

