7.3 Exploratory Objectives

The exploratory objectives are to evaluate the following:

- Severity of AKI post-cardiac surgery through Day 7.
- Mean increase in serum creatinine post-cardiac surgery through Day 7 or until Discharge if prior to Day 7.
- Occurrence of MAKE30 and MAKE90 post-cardiac surgery.
- Proportion of subjects experiencing MAKE30.
- Proportion of subjects experiencing MAKE90.
- Days on ventilator.
- Days in ICU.
- Hospital length of stay.
- Readmission rate.
- Changes in biomarkers of RBT-1 activity and/or kidney function.

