9.7.4 Visit 2 (Day 1)

9.7.4.1 Prior to Cardiac Surgery

The following procedures will be performed prior to the scheduled cardiac surgery on Day 1:

- Record changes in concomitant medications.
- Perform physical examination.
- Record vital signs.
- Obtain blood samples for serum chemistry, hematology, and blood biomarker testing.
- Obtain urine sample for urinary biomarker testing.
- Solicit any adverse events.

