11.1 Criteria for Evaluation

Efficacy assessments include the following:

- Change in preconditioning plasma biomarkers from Baseline (pre-dose) through Day 1 pre-op:
 - HO-1, ferritin, and IL-10
- Change in renal tubular injury biomarkers post-cardiac surgery through Day 3:
 - KIM-1, cystatin C, and NGAL

- Reduction in urine output (documented oliguria of <0.5 mL/kg/hour, not due to urinary tract obstruction) for more than 6 hours post-cardiac surgery through Day 3.
- Incidence of AKI post-cardiac surgery through Day 5, defined as:
 - An absolute increase in serum creatinine by 0.5 mg/dL, which is present over 2 laboratory measurements at least 12 hours apart; or
 - An increase in serum creatinine $\geq 1.5X$ Baseline.
- Severity of AKI post-cardiac surgery through Day 7.
- Average increase in serum creatinine post-cardiac surgery through Day 7 or until Discharge if prior to Day 7.
- Occurrence of MAKE30 and MAKE90 post-cardiac surgery.
- Proportion of subjects experiencing MAKE30.
- Proportion of subjects experiencing MAKE90.
- Days on ventilator.
- Days in intensive care unit.
- Hospital length of stay.
- Readmission rate.
- Changes in biomarkers of RBT-1 activity and/or kidney function.

Safety assessments include the following:

- Adverse events.
- Laboratory data and vital signs at regular intervals.

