## 2.2 Study Objectives

The overall objective is to evaluate the effect of RBT-1 on preconditioning response biomarkers in subjects undergoing CABG and/or cardiac valve surgery.

The primary objective is to evaluate the efficacy of RBT-1 in generating a preconditioning response as measured by a composite of plasma biomarkers (plasma heme oxygenase-1 [HO-1], ferritin, and interleukin-10 [IL-10]) from Baseline (pre-dose) through Day 1 PreOp.

The secondary objectives are to evaluate the efficacy of RBT-1 on the following:

- Change in renal tubular injury biomarkers post-cardiac surgery through Day 3
- Reduction in urine output (documented adverse event [AE] of sustained reduction in urine output, oliguria, or anuria) post-cardiac surgery through Day 5
- Incidence of AKI (defined as a  $\geq 1.5X$  baseline, i.e., a 50% increase from baseline in serum creatinine; documented AE of sustained reduction in urine output, oliguria, or anuria; or initiation of dialysis) post-cardiac surgery through Day 5

The exploratory objectives are to evaluate the following:

- Severity of AKI post-cardiac surgery through Day 7
- Mean increase in serum creatinine post-cardiac surgery through Day 7 or until Discharge if prior to Day 7
- Occurrence of MAKE – death, need for dialysis, and persistent renal dysfunction ( $\geq 25\%$  decrease in estimated glomerular filtration rate [eGFR]) – post-cardiac surgery through Day 30 (MAKE30) and Day 90 (MAKE90) post-cardiac surgery
- Proportion of subjects experiencing MAKE30
- Proportion of subjects experiencing MAKE90
- Days on ventilator
- Days in intensive care unit (ICU)
- Hospital length of stay
- Readmission rate
- Changes in biomarkers of RBT-1 activity and/or kidney function

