### **6.4 Laboratory Parameters**

Screening laboratory samples will be processed at a local laboratory. All other laboratory samples will be processed at a central laboratory. For subjects who will be administered study drug on the same day of Screening, blood and urine samples will need to be collected for central laboratory analysis in accordance with Visit 1a.

Serum chemistry and hematology will be measured at Screening (Visit 0), Visit 1a, Day 1 PreOp (Visit 2), and on Days 2 to 7 (or discharge, whichever is earlier; Visits 3-8), Day 30 (Visit 9), Day 60 (Visit 10), and Day 90 (Visit 11). Serum CysC will only be measured at Visit 1a and on Days 30 (Visit 9) and 90 (Visit 11).

Serum chemistry parameters include total protein, albumin, bicarbonate, blood urea nitrogen (BUN), serum creatinine, total bilirubin, alkaline phosphatase, glucose, sodium, potassium, phosphate, calcium, magnesium, gamma-glutamyl transferase (GGT), alanine aminotransferase (ALT), aspartate aminotransferase (AST), and CysC.

Hematology parameters include RBC, hemoglobin, hematocrit, MCV, MCH, MCHC, platelets, MPV, RDW and WBC.

Blood and urinary biomarkers will be collected at Visit 1a, 1b, 2 (PreOp, 1h PostOp, 12h PostOp), 3 (Day 2) and 4 (Day 3).

Blood biomarkers include preconditioning response biomarkers (plasma HO-1, ferritin, and IL-10) and other biomarkers of RBT-1 activity and kidney function.

Urinary biomarkers include tubular injury biomarkers (KIM-1, CysC, and NGAL) and other biomarkers of RBT-1 activity and kidney function, which include but are not limited to urine albumin to creatinine ratio (UACR), urine protein to creatinine ratio (UPCR), beta-2-microglobulin, osteopontin, calbindin, clusterin, and VEGF.

Blood and urine samples may be collected by remote phlebotomy, such as through a mobile phlebotomist or other blood collection center, for a visit conducted virtually on Day 7, 30, 60, or 90.

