### 7.5.3.2 Mean increase from baseline in serum creatinine

Mean changes and % mean changes from baseline (defined as Visit 1a) to the mean of creatinine PostOp through Day 7 (or discharge if earlier) will be summarized by treatment group. The between active treatment and placebo difference in mean change and % mean change will be analyzed using ANCOVA with treatment as main effect and baseline as a covariate. LSM difference and the associated 95% CI will be presented.

Additionally, the CMH test stratified by the baseline creatinine in approximately tertile ( $\leq 0.9$ ,  $>0.9$  to  $1.2$ ,  $>1.2$  mg/dL) will be carried out as a sensitivity analysis.

Analysis of change and % change from baseline to each post-dose visit through Day 90 (i.e., Days 1, 2, 3, 4, 5, 6, 7, 30, 60, and 90) will be analyzed using the mixed effects model for repeated measures (MMRM), which includes treatment, visit, and treatment-by-visit interaction as factors, baseline as a covariate, and subject as repeated measure unit. The LSM and 95% CI will be presented for each treatment group at each time point. In the computation, the variance-covariance matrix will be assumed AR(1) structure and the denominator degrees-of-freedom will be estimated using the improved Kenward-Rodger method. LSM and 95% for the between active dose and placebo group difference will also be presented at each time point.

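### SAP 5.3.2 defines the mean creatinine increase from all post-baseline values, which takes in the Day 1 PreOp sample, while the rest of the plan uses post-operative values only

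*SAP*

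**What the plan says.** SAP 5.3.2 takes "the average of the post-baseline serum creatinine through Day 7 or Discharge", whichever comes first, and subtracts baseline. It then fixes the reference point: "Baseline is defined as the serum creatinine collected at Visit 1a time point". Visit 1a is before dosing, 24 to 48 hours ahead of surgery.

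The analysis section describes a different average. SAP 7.5.3.2 summarises the change from the same Visit 1a baseline "to the mean of creatinine PostOp through Day 7 (or discharge if earlier"). The SAP abbreviation list gives PostOp as after cardiac surgery, so PostOp and post-baseline do not mean the same thing.

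The objectives and criteria agree with 7.5.3.2. SAP 2.2 has "Mean increase in serum creatinine post-cardiac surgery through Day 7 or until Discharge if prior to Day 7", Protocol 7.3 has "Mean increase in serum creatinine post-cardiac surgery through Day 7" and Protocol 11.1 has "Average increase in serum creatinine post-cardiac surgery through Day 7 or until Discharge if prior to Day 7". The title of Table 14.2-5.1, where the result will be reported, also says PostOp.

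On sampling, SAP 6.4 states: "Serum chemistry and hematology will be measured at Screening (Visit 0), Visit 1a, Day 1 PreOp (Visit 2), and on Days 2 to 7". Protocol 9.7.4.1 confirms the pre-surgery draw on Day 1: "Obtain blood samples for serum chemistry, hematology, and blood biomarker testing". The list of Day 1 procedures after surgery (Protocol 9.7.4.2) contains no chemistry.

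**The concern.** The two SAP sections select different samples. Under 5.3.2 the first value averaged is Day 1 PreOp, taken after dosing but before the surgical insult. Under 7.5.3.2 it is Day 2. A programmer who derives the variable from the endpoint-definition section would include a value that cannot reflect surgical injury, and would report it in a table whose title says PostOp.

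The protocol does not formally settle this, because SAP Section 1 says the SAP prevails where the two differ, and the SAP does not say which of its own sections governs. What is at stake is the size of the reported creatinine rise. The same ambiguity can reach eGFR, because SAP 7.5.3.3 analyses eGFR in the same way as creatinine.

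**Working it through.** The plan gives no effect size, SD or power for this endpoint, so there is no stated figure to reproduce. The check is direct arithmetic on the visit schedule.

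**Inputs from the documents**
- Baseline is Visit 1a (SAP 5.3.2).
- Later chemistry is on Day 1 PreOp, then Days 2 to 7 or discharge (SAP 6.4).
- Under SAP 7.2, a discharge value from Day 4, 5 or 6 is reported as Day 7, and a Day 7 value that is still missing is imputed with the last value from Days 3 to 6.

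**Inputs assumed, because the documents give no figure**
- c, the change from Visit 1a to Day 1 PreOp: 0 mg/dL, with a range of -0.05 to +0.10.
- r, the subject's mean post-operative change: 0.30 mg/dL, for illustration.

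**Formulas.** With k post-operative values, the 7.5.3.2 mean is r and the 5.3.2 mean is (c + k·r)/(k+1). The PreOp value has weight 1/(k+1). The shortfall is (r - c)/(k+1), or as a proportion of r, (1 - c/r)/(k+1). With c = 0 the proportion is 1/(k+1) whatever r is.

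**Weight of the PreOp value (equal to the shrinkage when c = 0)**

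| Last in-hospital value | k | Weight | Weight if that value is also counted as Day 7 |
|---|---|---|---|
| Day 3 | 2 | 1/3 = 33.3% | 1/4 = 25.0% |
| Day 4 | 3 | 1/4 = 25.0% | 1/5 = 20.0% |
| Day 5 | 4 | 1/5 = 20.0% | 1/6 = 16.7% |
| Day 6 | 5 | 1/6 = 16.7% | 1/7 = 14.3% |
| Day 7 | 6 | 1/7 = 14.3% | not applicable |

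**In mg/dL, with r = 0.30 and c = 0.** Day 4 discharge: (0 + 3 × 0.30)/4 = 0.225. Day 7: (0 + 6 × 0.30)/7 = 0.257. The 7.5.3.2 definition gives 0.30 for both.

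**Sensitivity to c.**
- Day 4 discharge: c = -0.05 gives 0.85/4 = 0.2125 (29.2% shrinkage); c = +0.10 gives 1.00/4 = 0.25 (16.7%).
- Day 7: c = -0.05 gives 1.75/7 = 0.25 (16.7%); c = +0.10 gives 1.90/7 = 0.271 (9.5%).

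**Artefact from unequal stay**, with the same true rise of 0.30 in both groups, c = 0 and no duplicate Day 7 value. If one group all leave on Day 4 and the other all stay to Day 7, the difference is 0.257 - 0.225 = 0.032 mg/dL. If 50% versus 25% leave on Day 4 and the rest stay to Day 7, it is 0.25 × 0.032 = 0.008 mg/dL.

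**Power** (illustrative; an unadjusted two-group comparison assuming between-subject SD 0.3, day-to-day SD 0.1, true difference 0.1 mg/dL and 42 per group). The variance of the change is 0.09 + 0.01/k + 0.01 for the post-operative mean, and (k/(k+1))² × 0.09 + 0.01/(k+1) + 0.01 for the 5.3.2 mean, whose expected difference is 0.1 × k/(k+1).
- k = 3: 0.100/0.3215 = 0.311 versus 0.075/0.2512 = 0.299. Power is about 29.7% versus 27.7%.
- k = 6: 0.100/0.3189 = 0.314 versus 0.0857/0.2785 = 0.308. Power is about 30.1% versus 29.2%.

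The SD shrinks along with the mean, so the loss is about 1 to 2 percentage points.

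**The case against.** The best reply is that the intent is clear. One phrase in 5.3.2 stands against both sets of objectives, the protocol's evaluation criteria, the analysis section and the table title, so the PreOp value enters only if someone follows the outlier. That is a fair argument for treating this as minor. It does not remove the conflict, because 5.3.2 is the section that defines the derived variable.

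A reader might infer that 5.3.2 makes the endpoint seriously dependent on length of stay, with early discharges diluted most. The documents do not support stating it that strongly, for three reasons.
- The gradient depends on how SAP 7.2 is applied. If the discharge value is also counted as Day 7, the range for discharge on Days 4 to 6 narrows to 20.0% to 14.3%. If the intervening days were filled in as well, every subject would have six post-operative values and a weight of 14.3%, with no gradient. SAP 5.3.2 stops at discharge, which leaves room for the shorter count, but the SAP does not settle it.
- The percentages equal the shrinkage only if the PreOp change is zero, and no figure for that change is given. The absolute loss also depends on each subject's own rise.
- A post-operative mean taken from Day 2 to discharge covers a different window for each subject in any case. If creatinine varies over those days, the 7.5.3.2 definition also depends on discharge day.

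The stakes are also low. The endpoint is exploratory, the interim comparison uses the primary endpoint, and the by-visit mixed model in 7.5.3.2 gives Days 2 to 7 separately without averaging in the PreOp value.

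**Conclusion.** The point holds as a conflict between two definitions of one exploratory endpoint. Followed literally, 5.3.2 averages in a pre-surgery value and understates the post-operative rise whenever the PreOp change is smaller than that rise. With a PreOp change of zero, the understatement is about 14% for a full set of Days 2 to 7 and 25% for a Day 4 discharge, or 20% if the discharge value is also counted as Day 7. The weights follow from the visit schedule; the zero PreOp change and all mg/dL figures are assumptions. Power is barely affected, and an artefactual group difference from unequal stay would be small (0.008 to 0.032 mg/dL in the examples). This is a low-severity correction, worth making before unblinding so that no one has to choose between two derivations afterwards.

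**What to change.** In SAP 5.3.2, replace post-baseline with post-operative (Day 2 onward), keeping Visit 1a as baseline, so that the definition matches SAP 2.2, SAP 7.5.3.2, Table 14.2-5.1 and the protocol. State in 7.5.3.3 that the mean eGFR change uses the same window. It would also help to say whether a discharge value reported as Day 7 under SAP 7.2 is counted once or twice in the average. The by-visit model can keep Day 1 as a post-dose visit, since it does not average across visits.

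The cost is a few words in the SAP, with no new data and no change to the planned tests. The edit removes the pre-surgery value. It does not make the mean independent of discharge day, and the report should not claim that it does.
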